9.6 INSURANCE AND LIABILITY

Terms will be included in the research agreement.

9.7 STUDY REPORT

9.7.1 Clinical Study Report

The results of the study will be reported in a Clinical Study Report (CSR). This report will be prepared in co-operation with DuPont Nutrition and Health, Kantvik Active Nutrition team. In compliance with the regulations, the final report will be produced within one year of completing the study. The final report will be provided to all investigators having included subjects in the study. The CSR will be provided in printing and as Word and PDF files.

9.8 PUBLICATION AND DATA RIGHTS

Terms for scientific publications are recorded in Research Agreement.

## 1 Abbreviations

AE	Adverse event
ANOVA	Analysis of variance
ATC	Anatomical Therapeutic Chemical Classification System, (a WHO drug classification system)
IL-8	Interleukin-8 assay
ITT	Intention-to-treat
MedDRA	Medical dictionary of regulatory authorities
PP	Per-protocol
qPCR	Quantitative polymerase chain reaction
RM-ANOVA	Repeated measures analysis of variance model
SAE	Serious adverse event

## 2 Study objective(s)

The primary objective of this study is to investigate the effect of probiotic *Bifidobacterium animalis* subsp. *lactis* Bl-04 on incidence of rhinovirus-associated common cold illness episodes in comparison with placebo. The results of this study should permit the decision of whether probiotic supplementation reduces the incidence of rhinovirus induced cold episodes compared to placebo.

The secondary objectives of this study are to investigate the effect of probiotic supplementation on the infection rate and duration of illness episodes, examine the effect of the probiotic on the rhinovirus load in the nose and to study the safety and tolerability of the product.

## 3 Design and type of the study

This is a phase II randomized, double-blind, placebo-controlled study of probiotic *Bifidobacterium animalis* subsp. *lactis* Bl-04 on incidence of common cold illness episodes induced by rhinovirus in healthy adults.

## 4 Sample size considerations

A total of 220 subjects were to be challenged and distributed in two groups of equal sizes to the two treatment groups. Based on the sample size calculations 95 completed subjects/ arm would be expected to detect a reduction in rhinovirus-induced illness of 20% (from 60% to 40%) with 80% power with  $p_{\alpha} = 0.05$ .

During the study, to ensure reaching the target sample size of completed subjects in the primary analysis population (Per Protocol dataset), the number of challenged subjects was decided to be increased to 254 in total.

## 5 Statistical hypotheses

The purpose of this study is to support the evidence that the probiotic supplementation is more effective than the effect of placebo in reducing the incidence of rhinovirus-associated illness episodes, i.e., the null-hypothesis to be tested is

$H_0$  : There is no relationship between the treatment and the incidence of rhinovirus-associated illness episodes

$H_1$  : There is a relationship between the treatment and the incidence of rhinovirus-associated illness episodes

The effect of probiotic supplementation is considered shown if the two-sided p-value of the primary statistical analysis is less than 0.05.

## 6 Analysis sets

### 6.1 Safety dataset

All randomised subjects receiving the study products will be included in the safety dataset.

### 6.2 Intention-to-treat (ITT) dataset

The ITT dataset will consist of all subjects having been randomized to a treatment (Safety dataset) and receiving the virus challenge on Day 0 per exclusion criteria defined in the protocol. This population will be used for all efficacy analyses (see 20.2.).

### 6.3 Per protocol (PP) dataset

The PP dataset will consist of all subjects having been randomized to a treatment and receiving the virus challenge on Day 0 (ITT), without any major protocol violation. Subjects with acute neutralizing titer of  $>1:4$ , respiratory virus detected prior to virus and antibiotic use before day 14 will be excluded, and only subjects with study product compliance of  $>80\%$  will be included. The subject classification to PP dataset will be done before opening of the randomisation code. PP dataset is used for all efficacy and exploratory analyses as the primary dataset, thus also for the primary evaluation of study hypothesis (see 20.2.).

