3.4 Subject Withdrawal and replacement of subjects

3.4.1 *Withdrawal criteria*

Subjects may be withdrawn from the study (i.e. from any further study product or study procedure but not from analyses) for the following reasons:

- At their own request or at the request of their legally authorized representative.
- If, in the investigator's opinion, continuation in the study would be detrimental to the subject's well-being.
- If they are lost to follow-up.

In all cases, the reason for and date of withdrawal must be recorded in the eCRF and the sponsor's representative must be notified within 5 days. The subject must be followed up to establish whether the reason was an adverse event, and, if so, this must be reported.

The investigator must make every effort to contact subject lost to follow-up. Attempts to contact such subject must be documented in the subject's records (e.g., dates and times of attempted telephone contact).

Any subject may be withdrawn from the study at the discretion of the investigator. The subject is also free to terminate his participation at any time. An end of study visit will then be organized.

3.4.2 *Withdrawn subject data collection*

The principal investigator and/or other investigator involved in the study will document on the termination page of the eCRF the reason for the subject withdrawal as follows:

- Lost to follow-up: subjects who leave the study unnotified or do not attend the study visit or cannot be contacted by phone. Intensive efforts should be made to locate and recall them if possible and to determine their health status at a minimum.
- Adverse event: an adverse event form must be completed.
- Adverse laboratory event: this reason should be stated when a laboratory value is interpreted as a clinically significant abnormal value not explained by a laboratory error or being not a known or abnormal value commonly observed in this type of population.
- Deviation from protocol.
- Consent withdrawn.
- Other: if no above mentioned reasons are applicable, then the reason will be specified.

3.4.3 *Replacement of subjects*

Subjects withdrawn from the study will not be replaced.

4 Experimental Design

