4.1.1 Number of subjects

Approximately 900 volunteers will be recruited for participation in these studies. Volunteers seronegative to rhinovirus type 39 will be randomly treated for 42 days with either:

- probiotic (n=130)
- placebo (n=130)

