4.2.7 Assessment of Compliance (Study Days -21,-14,-7, and 0-14)

At each study visit during the pre-challenge dosing period, volunteers will be asked to return unused study product to the study site. Compliance will be assessed by counting missed doses of study product. For purposes of the per protocol analyses, the subject will be assessed as compliant with the protocol if at least 80% of the planned doses were taken. In addition, DuPont Nutrition and Health will measure the amount of *Bifidobacterium animalis* subsp. *lactis* from the fecal samples using qPCR.

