7.1.2 Assessment of Adverse Events

For the purposes of this study using experimental rhinovirus infection, physical signs and symptoms that are expected to be associated with the common cold should not be reported as adverse events. The following physical signs and symptoms are expected to be associated with the common cold: nasal obstruction (nasal stuffiness), coryza (runny nose), sore throat, cough, sneezing, myalgia, headache, feverishness, chills, loss of appetite and malaise.

Information regarding common cold-related complications must be documented appropriately. Common cold-related complications include bronchitis, bronchospasm or exacerbation of asthma, sinusitis and otitis media. For common cold-related complications, the following information should be documented: onset date, severity, seriousness, relationship to study therapy, action taken regarding study therapy, outcome, and therapy given for event.

Some subjects may experience gut discomfort during the study product consumption. The symptoms that have been associated with use of bifidobacteria include bloating, flatulence and abdominal pain. The subjects should contact the study staff in the case that symptoms persist.

Assessment of all adverse events will include recording the time of onset and resolution of the event, severity, intervention, and an attribution by the investigator of whether the event was related to the study product.

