## 10 Extent of exposure and compliance

Extent of exposure will be evaluated descriptively as duration of study treatment (number of days).

Compliance will be assessed by summarizing the number of used and unused sachets returned as percentages of the total number of sachets dispensed. Product recovery from fecal samples will be evaluated by qPCR.

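### The primary superiority test runs in a per-protocol set whose antibiotic and compliance rules can remove subjects after their Day 1-5 symptoms have been scored

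*SAP*

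**What the plan says.** SAP 6.3 and table 20.2 make PP the main set for the primary endpoint: "PP dataset is used for all efficacy and exploratory analyses as the primary dataset, thus also for the primary evaluation of study hypothesis". PP starts from the challenged subjects (the SAP's ITT set). Those with "respiratory virus detected prior to virus and antibiotic use before day 14 will be excluded, and only subjects with study product compliance of" more than 80% are retained. Classification is to be done before the randomisation code is opened. Table 20.2 also runs the primary endpoint in ITT, marked as a secondary analysis.

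SAP 6.3 gives no period over which compliance is counted. The protocol section is headed "Assessment of Compliance (Study Days -21,-14,-7, and 0-14" and says that, for per-protocol purposes, "the subject will be assessed as compliant with the protocol if at least 80% of the planned doses were taken". SAP 10 describes a summary on a different base: "Compliance will be assessed by summarizing the number of used and unused sachets returned as percentages of the total number of sachets dispensed".

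SAP 11.1 requires two things for an illness episode: a symptom criterion over Days 1-5, and infection, shown either by virus isolation on Days 1-5 or by Day 28 serology.

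On withdrawal, Protocol 3.4.1 says: "Subjects may be withdrawn from the study (i.e. from any further study product or study procedure but not from analyses". Protocol 5.4 says that volunteers who take antibiotics during the study are taken out of it. Protocol section 8 does not name a primary analysis set.

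**The concern.** In a superiority trial the primary set should not depend on events that the outcome can cause. An antibiotic course on Days 6-13 or sachets missed on Days 6-14 cannot change a Day 1-5 symptom score, but the illness behind that score may lead to either. Protocol 7.1.2 expects complications of the induced cold: "Common cold-related complications include bronchitis, bronchospasm or exacerbation of asthma, sinusitis and otitis media". These are plausible reasons for an antibiotic prescription. That is inference, as is the idea that someone who feels ill may stop taking sachets; the documents state neither.

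If such exclusions fall differently on ill subjects in the two arms, the groups compared are no longer those that randomisation produced. A difference in illness rates can then appear, or be hidden, without any product effect. Classifying subjects before unblinding prevents deliberate selection, but not selection that works through the illness itself.

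**Working it through.** **1. The plan's sample size.** Inputs from SAP 4 and 5: 60% v 40%, two-sided alpha 0.05, power 80%. Unpooled formula: n = (1.960 + 0.842)² × (0.6×0.4 + 0.4×0.6) / 0.20² = 94.2, so 95 per arm, as stated. (The pooled-variance form gives 97.)

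**2. Room for exclusions.** SAP 4 raised the number challenged from 220 to 254 to secure 2 × 95 = 190 in PP. That allows for 254 − 190 = 64 exclusions, or 25.2%. At 220 it was 30, or 13.6%.

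**3. Can stopping after Day 5 alone decide PP membership?** Day -28 to Day 14 inclusive is 28 + 1 + 14 = 43 days, but Protocol 4.1.1 says subjects "will be randomly treated for 42 days with either" product. Day -28 to Day 5 inclusive is 34 days. For a subject who takes every dose through Day 5 and none after:

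| Counting | Compliance | PP status |
|---|---|---|
| 34 of 43 | 79.1% | excluded |
| 33 of 42 (first dose the day after the visit) | 78.6% | excluded |
| 34 of 42 | 81.0% | kept |

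The documents do not say which count applies. One further sachet keeps the subject in on the 43-day count (35/43 = 81.4%).

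**4. At least 80% v more than 80%.** With 42 or 43 planned doses the cut-offs are 33.6 and 34.4, so no whole number of doses falls exactly on 80% and the two rules agree. They can differ for other denominators, such as 32/40.

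**5. Effect on the type I error.** Assumptions: no product effect, 60% ill in both arms, 127 challenged per arm (254/2), and a share q of ill subjects removed from one arm only. Apparent illness rate in that arm = 0.6(1 − q)/(1 − 0.6q); number left = 127(1 − 0.6q), rounded. The rejection rate is the exact sum of binomial probabilities over all tables where the uncorrected chi-square exceeds 3.84.

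| q, one arm only | Left in that arm | Apparent rates | Two-sided rejection |
|---|---|---|---|
| 0 | 127 | 60.0% v 60.0% | 4.9% |
| 0.05 | 123 | 58.8% v 60.0% | 5.6% |
| 0.10 | 119 | 57.4% v 60.0% | 7.4% |
| 0.20 | 112 | 54.5% v 60.0% | 13.8% |

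If ill subjects are removed from both arms, 10% and 10%, or 20% and 20%, gives 5.1%; 10% v 5% gives 5.4%.

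**6. Power of a larger primary set** (same exact method). 95 per arm, 60% v 40%: 79.3%. 127 per arm, 60% v 40%: 89.7%. 127 per arm, effect diluted to 18 points (60% v 42%): 82.6%.

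**The case against.** The best defence is that PP is openly declared as primary and sized for in SAP 4, is classified blind, and is accompanied by an ITT analysis of the same endpoint. Protocol 4.2.7 itself foresees an 80% rule for per-protocol analyses. All of this is correct. It lessens the problem without removing it, because the hypothesis is still judged on PP and the SAP does not say what follows if PP and ITT disagree.

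Several stronger readings are tempting, but the documents do not support them:

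- *The whole primary outcome precedes the exclusions.* Only the symptom component is complete at Day 5. Day 28 serology can still establish infection.
- *The compliance rule breaks the protocol's withdrawal rule.* Low compliance is not withdrawal. The tension with Protocol 3.4.1 concerns antibiotic users withdrawn under Protocol 5.4, and only in the primary analysis, since they remain in the secondary ITT analysis.
- *SAP 15 hides a deviation.* Protocol section 8 names no primary set and leaves detail to the SAP, so there is no stated set to deviate from.
- *Compliance has two competing denominators.* SAP 10 describes a summary; Protocol 4.2.7 states the PP rule. The mismatch in the rule itself is at least 80% against more than 80%.
- *The error rate is certainly above 5%.* That requires exclusion to depend jointly on arm and illness. A difference in tolerability unrelated to illness does not inflate the error when there is no effect.
- *The earlier challenge trial shows the mechanism.* Protocol 1.1 implies that 15 of 73 probiotic (20.5%) and 22 of 79 placebo subjects (27.8%) were left out of its analysis, but gives no reasons. Losses were higher on placebo, which does not fit a tolerability explanation, although Table 1 reports gastrointestinal events only in the active arm.

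**Conclusion.** The concern holds in this form: the primary superiority test rests on a set from which challenged subjects can be dropped after their symptom score is fixed, for reasons the illness may produce. The antibiotic rule does this on the face of SAP 6.3. The compliance rule does so if the Protocol 4.2.7 period applies, and then turns on an undefined dose count.

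The size is conditional. Reaching 7.4% or 13.8% takes about 8 or 15 ill subjects removed from one arm and none from the other. Balanced removal leaves the error near 5%, and 10% v 5% gives 5.4%. The documents give no basis for estimating the real pattern, so the finding is that the 5% level is not protected, not that it is breached. The fault still merits correction before unblinding, because the remedy is wording and the primary set becomes larger.

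**What to change.** - **Primary set.** In SAP 6.3 and table 20.2, run the primary test on all randomised and challenged subjects, analysed as randomised, whatever their later antibiotic use, compliance or withdrawal. The Day 0 titre and pre-challenge virus restrictions may be kept, since they precede the outcome. They still follow randomisation at Day -28, so the result in all challenged subjects (ITT) must be reported beside the restricted one.
- **PP as supportive.** Count its antibiotic and compliance criteria only through Day 5. State one compliance threshold, the denominator and how planned doses are counted.
- **Reconcile the passages.** Protocol 3.4.1, Protocol 5.4 and SAP 6.3 must agree on whether subjects who leave because of antibiotics stay in the primary analysis. Because SAP 7 allows no imputation, also say how infection is classified when such a subject has no Day 28 titre.
- **Record the change** in SAP 15.

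The cost is SAP wording and no extra subjects. The downside is slight dilution from non-compliers: even if the effect falls to 18 points, power is about 83% with 127 per arm, against 79% for the undiluted effect with 95. If the Day 0 restrictions are kept, the set will be somewhat below 127 per arm and the gain smaller. Subjects lost between Day -28 and challenge remain outside every efficacy set in the SAP; this change does not address them.

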### 6.4 Infected dataset

The Infected dataset will consist of all subjects in the PP dataset, who got infected with the challenge virus. Infection will be defined as the isolation of the challenge virus on any of the 5 days (study days 1-5) after virus challenge or a four-fold rise in neutralizing antibody titer to the study virus. The Infected dataset will be used for analysis of e.g. symptom score, viral load and exploratory analyses (see 20.2).

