#### 11.2.3 Viral load during infection

Viral load will be assessed by comparing the quantitative virus titer in nasal lavage between the probiotic and placebo groups. For this calculation, subjects with no virus isolate on a study day will be defined as having a quantitative titer of  $-0.5$  ( $\log_{10}$ ).

The quantitative viral titer load during infection will be evaluated with repeated measures analysis of variance model (RM-ANOVA) including the daily titer load as a response ( $\log_{10}$ ), treatment, day and the interaction of day and treatment as explanatory variables. The random effect of subject will be included in the model. Model assumptions will be checked with model diagnostics and normality plots. In case the assumptions of the RM-ANOVA model are severely violated (after common transformations), generalised linear mixed models for repeated measurements with more appropriate distribution assumptions (e.g. poisson or negative binomial) will be fitted. The main interest of this analysis is the overtime treatment effect.

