#### 11.2.4 Proportion shedding the virus

Virus shedding will be defined as the isolation of the challenge virus on any of the 5 days (study days 1-5) after virus challenge.

Proportion shedding the virus will be analysed exactly the same way as the primary response (section 11.1).

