### Blood transcriptomics

For blood transcriptomics at least the following analyses will be conducted. The PP population will be primarily used.

Unsupervised clustering of the samples will be conducted. Clustering will be done at DuPont and in case clusters are formed, the clustering information (per sample per subject) will be provided to 4Pharma for further the analyses described below.

- Timepoint and treatment effect on clustering will be investigated with categorical repeated measures models, where clustering is the outcome variable, and timepoint, treatment, interaction of treatment and timepoint are included as fixed effects.
- Effect of cohort, infection (yes/ no) and illness (yes/ no) on clustering will be investigated with the above described model by including separately each factor to the analysis model.
- The effect of D-28/D0 clustering on the following outcome variables will be investigated by adding the cluster as a fixed effect to the analysis models: Duration of illness, viral shedding, clinical symptom severity score and immune markers. For symptom scores, the analysis models have already been described in 11.2.5 and 11.2.6. Also, for immune markers the analysis model to be used has already been described in this chapter. For duration of illness an analysis of covariance (ANCOVA) model will be used including treatment and cluster effect in the model. The analysis will be conducted using the Ill population. For viral shedding a logistic regression model with treatment and cluster effect will be fitted and infected population used. For all models, also fixed interaction effect of treatment and cluster may be investigated.

In addition to the clustering, correlations between individual genes from throat and nasal metagenomics will be calculated, if feasible. For the correlations FDR correction will be used with the p-values.

Connections between the exploratory data/ results and efficacy and other endpoints may be investigated with suitable analysis models (will be described in the Documentation of the Statistical Methods, if done). Part of the exploratory analyses (microbiota and transcriptomics) will not be included in the Statistical Study Report.

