## 20.2 Analyses per dataset

The following datasets will be used primarily for the analyses. For exploratory and post-hoc analyses also other datasets may be used.

	Variable	Dataset				
		ITT	PP	Inf.	Ill	Safety
Primary	Incidence of rhinovirus-associated illness episode	x	X			
Secondary	Duration of illness	x	x		X	
	Incidence of infection	x	X			
	Viral load	x	x	X		
	Proportion shedding	x	x	X		
	Total symptom score (acute illness)	x	x	X		
	Total symptom score (illness)	x	x	X		
Exploratory	Each symptom score (eg rhinorrhea; sneezing, obstruction, sore throat)		x	X		
	IL-8 + cytokines		X	X		
	Ab response			X		
	Fecal samples - BI-04 PCR		X			
	Nasal swabs		X	x		
	Throat swabs microbiomics		X	x		

---

	Throat swabs culture	X	x		
	Transcriptomics	X	x	X	
Safety parameters					X

- **X** = main analysis; x = secondary analysis

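### The main shedding analysis uses the Infected dataset, whose definition contains the endpoint, so its bias is of unknown direction and it may be largely uninformative

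*SAP*

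**What the plan says.** SAP 6.4 builds the Infected dataset from the PP dataset: "Infection will be defined as the isolation of the challenge virus on any of the 5 days (study days 1-5) after virus challenge", or alternatively a four-fold rise in neutralizing titre. SAP 11.2.4 states: "Virus shedding will be defined as the isolation of the challenge virus on any of the 5 days (study days 1-5) after virus challenge". In SAP 20.2 the row "Proportion shedding" has its main-analysis mark under the Infected dataset, with PP and ITT marked as secondary. The exploratory transcriptomics text shows that this is intended and not a slip in the table: "For viral shedding a logistic regression model with treatment and cluster effect will be fitted and infected population used".

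Other text points to a wider set:
- SAP 6.3 names PP as the primary dataset for every efficacy analysis.
- SAP 11.2.4 and protocol 8.4.2 send shedding to the same analysis as the primary endpoint, whose main set in SAP 20.2 is PP.
- Protocol 6.3.4 compares the proportion of volunteers who shed in each group and does not restrict this to the infected.
- SAP 15, which lists departures from the protocol, does not mention the restriction.

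**The concern.** Isolation on days 1-5 is both the endpoint and one of the two ways into the denominator. A shedder cannot be outside the set. A non-shedder is inside it only by seroconverting without an isolate. A volunteer who is fully protected, with no isolate and no titre rise, leaves the numerator and the denominator together. The arms compared are then no longer the randomised arms. They are subgroups selected after randomisation on an outcome that the product is meant to change, and which is itself the second secondary endpoint.

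Shedding is fourth in the secondary hierarchy, ahead of the two symptom-score endpoints, and SAP 11.2 relies on that order in place of a multiplicity correction. A shedding result produced or erased by the choice of denominator therefore also affects what can be concluded about the endpoints below it.

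**Working it through.** **1. The plan's own figure.** SAP 4 gives 95 completed per arm for illness, "from 60% to 40%) with 80% power". SAP 5 sets the test: "The effect of probiotic supplementation is considered shown if the two-sided p-value of the primary statistical analysis is less than 0.05". With unpooled variance, n = (1.960 + 0.842)² × (0.24 + 0.24) / 0.20² = 94.2, so 95. The pooled formula gives 97, and power at 95 is then 79.2%. The figure reproduces. Neither document gives a power for shedding.

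**2. The effect size.** Protocol 1.1 reports shedding of 76% on probiotic and 91% on placebo in the earlier challenge trial, p=0.04. On the 58 and 57 volunteers analysed there, 44/58 = 75.9% and 52/57 = 91.2% give a Fisher p of 0.043, which matches. On the 73 and 79 challenged, the nearest counts (55 and 72) give 0.015, which does not. The rates therefore belong to the 58 and 57 who met that trial's analysis criteria.

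**3. Power in the PP set.** Mean rate 0.835. Pooled SE = √(2 × 0.835 × 0.165 / 95) = 0.0539. Unpooled SE = √((0.91 × 0.09 + 0.76 × 0.24) / 95) = 0.0527. z = (0.15 − 1.960 × 0.0539) / 0.0527 = 0.84, so power is 80.0%. Simulation under the SAP's rule (chi-square, or Fisher when an expected count is 5 or lower) gives about 81-82%.

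**4. Power in the Infected set, equal seroconversion.** Let p be the shedding rate and f the share of non-shedders with a four-fold rise. Then P(shed | infected) = p / (p + (1 − p)f). For f = 0.25, placebo is 0.91 / (0.91 + 0.09 × 0.25) = 97.6% and probiotic is 0.76 / (0.76 + 0.24 × 0.25) = 92.7%. The documents do not give f, so the whole range is shown. It starts from 95 PP subjects per arm, with several thousand simulated trials per row; ranges show the spread between repeat runs.

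| f, both arms | Placebo | Probiotic | Power, Infected set |
|---|---|---|---|
| 0 | 100% | 100% | 0% (no test possible) |
| 0.10 | 99.0% | 96.9% | 8% |
| 0.25 | 97.6% | 92.7% | 25-29% |
| 0.50 | 95.3% | 86.4% | 55-56% |
| 0.75 | 93.1% | 80.9% | 70-72% |
| 1 | 91% | 76% | about 81% |

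PP power does not depend on f.

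**5. Power in the Infected set, unequal seroconversion.** Suppose no placebo non-shedder seroconverts but some probiotic non-shedders do.

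| f placebo v probiotic | Placebo | Probiotic | Power, Infected set |
|---|---|---|---|
| 0 v 0.10 | 100% | 96.9% | 17% |
| 0 v 0.25 | 100% | 92.7% | 76-77% |
| 0 v 0.50 | 100% | 86.4% | 99% |
| 0 v 0.625 | 100% | 83.5% | 99.8% |

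In the last row infection is equal in the two arms (0.76 + 0.24 × 0.625 = 0.91), and the gap is 16.5 points against a true 15. The same formula can separate arms that shed equally: with 91% in both and f of 0 v 0.50, the Infected-set rates are 100% and 0.91 / (0.91 + 0.09 × 0.50) = 95.3%.

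**The case against.** **The test is not fully circular.** A reader might infer that the Infected-set analysis cannot show the earlier trial's effect. The documents do not support that. The antibody route keeps seroconverting non-shedders in the set, so the test collapses only if there are none. Protocol 1.1 reports no effect on serum antibody response in the earlier trial. That is compatible with a product that lowers shedding but not seroconversion, and in that case the Infected set could show the difference, even enlarged. This stands. It does not rescue the plan, because one and the same shedding effect gives anything from no test to near-certain significance, depending on an unstated quantity.

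**The earlier figures may already be conditional.** The documents do not say whether that trial's analysis criteria required infection. If they did, 91% and 76% are already rates among the infected, and the adjustment in step 4 would not apply to them. So the calculation is an illustration, and no claim can be made that the earlier effect came from a differently defined set.

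**The wider analyses are planned.** PP and ITT runs for shedding are in SAP 20.2, infection itself ranks higher with PP as its main set, and the primary endpoint is untouched. This stands and lowers the severity. But the prespecified conclusion follows the main analysis, and that is the Infected set.

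**The contradictions can be read down.** SAP 6.3 refers the reader to 20.2, and the wording in 11.2.4 might cover only the choice of test. Even so, protocol 6.3.4 is unrestricted and SAP 15 records no departure from it.

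**Viral load and symptom scores.** It is tempting to extend the criticism to these, since their main set is also the Infected one. But the protocol and SAP name the endpoint as viral load during infection, and SAP 6.4 assigns both measures to this set. That is a choice of question, and a power comparison would rest on assumed means and SDs. What stands is that such comparisons are not protected by randomisation.

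**The viral-load fallback.** SAP 11.2.3 says "generalised linear mixed models for repeated measurements with more appropriate distribution assumptions (e.g. poisson or negative binomial) will be fitted". The distributions are examples only, and the list of log, square-root and inverse transformations belongs to other endpoints. The point is minor: the two models named do not accept the −0.5 log10 value assigned to negative days.

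**Conclusion.** The point holds for proportion shedding and should be fixed. The main analysis conditions on a post-randomisation set defined in part by the endpoint, so the randomised comparison is lost, the bias has unknown direction and the test may be largely uninformative. With 91% v 76% and 95 per arm, PP power is about 81%. Infected-set power is 0% to about 81% with equal f, and 17% to nearly 100% when only probiotic non-shedders seroconvert.

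These sizes assume that the earlier rates apply to all PP subjects and treat f as unknown. The approximate 90% control infection rate in protocol 8.1 is too rough to fix f. The structural point rests on the definitions alone and needs none of these numbers. It concerns one secondary endpoint and its place in the hierarchy; it does not touch the primary endpoint.

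**What to change.** Before the code is opened:

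- In SAP 20.2, make PP the main set for proportion shedding with ITT alongside, so that volunteers without an isolate count as non-shedders. Drop the Infected set for shedding or label it descriptive only, and do the same in the transcriptomic shedding model. This brings the table into line with SAP 6.3, SAP 11.2.4 and protocol 6.3.4. If the restriction is kept instead, justify it and list it in SAP 15.
- For viral load and the two total symptom scores, report the planned PP and ITT results beside the Infected-set result, and state that the latter is not protected by randomisation.
- In SAP 11.2.3, require that any fallback model accept the −0.5 log10 value. A left-censored mixed model, or a Wilcoxon test on each subject's mean log10 titre over days 1-5, would do.

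The cost is SAP wording and one table. No new data are needed, and the PP and ITT runs are already planned.
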